## 14 DATA COLLECTION AND EVALUATION

The data questionnaires will be used both as initial patient registration form and as form for follow up evaluations during and after treatment.

Transmission of the data from collaborating institutions to the local subcenter will be made on data forms either by conventional mail, fax or by e-mail.

The subcenters and the study reference center will perform randomisation promptly after receiving the registration forms or the 6 week report forms from the referring institutions.

For evaluation, the completed questionnaire sheets are sent to the subcenters.

The local coordinator will be available for any clinical questions of the treating

physicians, and review the data sheets for completeness and correctness.

The data input into the uniform LCH III database will be performed at the local subcenter, if possible, or the revised data sheets will be transferred to the study reference center in Vienna.

For the regular study evaluations the local data bases will be transferred to the study reference center.

Access to common data from the study data base will be given only with the approval of the Scientific Committee and the permission of the Board of the Histiocyte Society.

## **15 DATA SAFETY MONITORING BOARD (DSMB)**

An independent Data Safety Monitoring Board composed of 4 international experts will monitor the progress of the study on ethical and scientific grounds. The role of the DSMB will be

- to review accrual rate and
- to be involved in all interim analysis. Five sequential analyses are planned, the results will remain confidential. Based on the results of the interim analysis the DSMB will recommend whether the study can continue or whether it must be amended or stopped prematurely.
- to monitor toxicity- biannually the DSMB will review the toxicity reports together with the study committee.

The DSMB will be asked to review any major modification to the study proposed by the study committee prior to its implementation.

## **16 STATISTICAL CONSIDERATIONS**

The study reference center in Vienna will carry out all analyses. The results and the data will be sent to the Institute of Medical statistics in Mainz for an independent statistical review after the interim-analyses and three weeks before a study committee meeting. The randomisation lists will be provided by the statistical center in Mainz.

## 16.1 DESIGN

### 16.1.1 Group 1 “RISK” patients

The Group 1-Study of LCH-III is a randomized controlled clinical trial for patients with multi-system LCH WITH involvement of “RISK” organs (hematopoetic system, liver, spleen or lungs). The random assignment to the treatment arms will be done in blocks, stratified according to local subcenters to ensure a balance within the local subcenters and within each pre-specified number of treatment assignments (=block). The randomization will be done in the local subcenter without delay after diagnosis.

### 16.1.2 Group 2 “LOW RISK” patients:

The Group 2-Study of LCH-III is a randomized controlled clinical trial for patients with multi-system LCH WITHOUT involvement of “RISK” organs (hematopoetic system, liver, spleen or lungs) and initial response at week 6 (NAD/AD better).

The random assignment to the treatment arms will be done in blocks stratified according to age at diagnosis ( $\leq 2$  years,  $> 2$  years) and local subcenters to ensure a balance within age groups, the local subcenters and within each pre-specified number of treatment assignments (=block). The randomization will be done in the local subcenter without delay after the first response evaluation 6 weeks after therapy start. Only patients with therapy response, i.e. regression (AD better) or resolution (NAD) after 6 weeks of initial treatment, will be eligible for randomization.

In addition, the impact of a prolonged initial treatment (= course2) for those patients who are not eligible for randomization is examined and compared with the historical control group of LCH-II patients.

## 16.2 ENDPOINTS

### 16.2.1 Primary endpoints

#### 16.2.1.1 Group 1 “RISK” patients:

The primary aim of the study is to compare the therapeutic efficacy of **control arm A** (PDN+VBL) with the **experimental arm B** (PDN+VBL+MTX). The primary endpoint is

the proportion of **non-responder in risk organs to the initial treatment.**

**Non-response** to initial therapy is defined as:

- death within 12 weeks of initial treatment or
- progression (worse) in risk organs at week 6
- lack of response (=intermediate response or progression) in risk organs at week 12 as compared to the status of disease at week 6

If the null hypothesis is true, the two randomized treatment arms are equally effective in terms of non-response. If the alternative hypotheses is true, there is a difference between the two randomized arms in terms of efficacy.

#### **16.2.1.2 Group 2 “LOW RISK” patients:**

The primary aim of the study is to compare the reactivation free survival rate in initial responders at week 6 with continuation treatment for 6 months (Arm LR 6) versus 12 months (Arm LR 12) in those patients without disease reactivation within the first 6 months.

If the null hypothesis is true, the reactivation rate of both randomized arms are equal. If the alternative hypothesis is true, there is a difference between the two arms in terms of reactivation frequency.

#### **16.2.2 Secondary endpoints**

- Overall survival
- Proportion of responders (overall and in risk organs) at week 6
- Proportion of responders (overall and in risk organs) at week 12
- Reactivation free survival after response at week 12
- Time to NAD
- Incidence of permanent consequences
- Toxicity
- Reactivation free survival after NAD (overall and in risk organs) and for “RISK” patients a historical comparison of Arm A of LCH III with Arm A of LCH-II with respect to the frequency of reactivation to evaluate the impact of the

prolonged study duration in risk patients

- Value of a prolonged initial treatment (course 2) of non-responding “LOW RISK” patients compared to a historical control of LCH-II patients without “RISK” organ involvement

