**Figure 2. Treatment plan LCH II**

A new stratification system was adopted, distinguishing between “RISK” patients with involvement of “RISK” organs like liver, spleen, lungs, hematopoetic system or age under 2 years, and “LOW RISK” patients without such organs involved and age beyond 2 years. “RISK” patients were eligible for the randomisation between the 2-drug and the 3-drug arm, “LOW RISK” patients received initial treatment according to the 2-drug arm only, and a continuation therapy without 6-MP.

Since the start of the LCH II study on 1st May 1996, 697 patients were registered on the LCH II Study. 321 patients had multisystem disease, 87 (27%) of these were stratified as “LOW RISK” patients, 233 (73%) patients were classified as “RISK” patients. Overall the compliance of the participating subcenters and clinics was not completely satisfying. Only 176 of these “RISK” patients were randomised (76%), 88 each to arm A and arm B. 66 (37%) of the “RISK” patients were under 2 years of age without involvement of “RISK” organs, of these only 41 (62%) were randomised. This points towards a poorer acceptance of the randomisation for this particular group of patients.

The results in the “LOW RISK” group were satisfying. There were 89%

responders, only one nonresponder at week 6, and no fatalities. Among 170 randomized “RISK” patients, in whom the response at week 6 was available, 113 (66%) were judged as responders. This compares favourably to the 6-week responder rate of 44% in the LCH I study, but is less than the 76% rate of responders in the DAL HX studies.

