## **5 STRATIFICATION**

### **5.1 GROUP 1 - MULTISYSTEM “RISK” PATIENTS**

Multisystem patients WITH involvement of one or more “RISK” organs i.e. hematopoietic system, liver, spleen or lungs

Patients with **single system lung** involvement are not eligible for randomisation

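### The historical test of longer treatment in Risk patients names LCH-II Arm A without limiting it to risk-organ patients, although LCH-II defined Risk more widely than LCH III

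*Protocol*

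**What the plan says.** Under reactivation free survival after NAD, Section 16.2.2 adds for Risk patients "a historical comparison of Arm A of LCH III with Arm A of LCH-II with respect to the frequency of reactivation". The stated purpose is to assess the impact of the "prolonged study duration in risk patients". No restriction is placed on the LCH-II arm. The next bullet, on course 2 in Low Risk patients, does define its control by organ status: "compared to a historical control of LCH-II patients without" risk-organ involvement. Section 16.3.2, on the secondary analyses, does not describe the Risk comparison.

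The two trials define Risk differently:

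- **LCH-II** (Section 2, text after Figure 2): involvement of "organs like liver, spleen, lungs, hematopoetic system or age under 2 years". Only Risk patients could be randomised. Of 233 such patients, 176 were randomised ("patients were randomised (76%), 88 each to arm A and arm B"). Sixty-six Risk "patients were under 2 years of age without involvement of" risk organs; "of these only 41 (62%) were randomised". Section 2 later counts 118 randomised Risk patients with risk organs.
- **LCH III Group 1** (Section 5.1): "Multisystem patients WITH involvement of one or more" risk organs. Section 2.1 drops age under 2 as a stratification criterion.

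**The concern.** A control arm that admitted young children without risk organs is not the same population as a treated arm that excludes them. A difference in reactivation could then reflect case mix as well as treatment.

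This comparison carries weight because both Group 1 arms are treated for 12 months in total (Section 9.1). No randomised contrast in Risk patients therefore tests duration. It is the only analysis in the protocol that addresses the reactivation part of goal 6.1.2, which is to reduce reactivations by prolonging continuation treatment to one year.

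There is a second, smaller difficulty. Section 6.1.1 introduces a second course of initial therapy as a measure in its own right, separate from the longer continuation treatment of Section 6.1.2. Arm A of LCH III gives that course to patients who are AD better or intermediate at week 6 (Section 9.1.1.2). A difference from LCH-II cannot then be credited to duration alone, as the wording of Section 16.2.2 implies.

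**Working it through.** **1. The protocol's own figures.** 41/66 = 62.1% (stated 62%) and 176/233 = 75.5% (stated 76%) both reproduce. The stated 37% for the 66 children matches 66/176 = 37.5% but not 66/233 = 28.3%. It is not used below.

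**2. Share of the named control outside Group 1.**
- From the 41 randomised: w = 41/176 = 23.3%. In an arm of 88, that is 0.233 × 88 = 20.5.
- From the 118 with risk organs: 176 − 118 = 58, so w = 58/176 = 33.0%, or 29 of 88.

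The two counts disagree (176 − 41 = 135, not 118), so a range is needed. If the 118 were counted only among the 170 patients with a week-6 response, the share would be 52/170 = 30.6%, inside that range. The split by arm is not given, so an even split is assumed. A restricted control would keep about 118/176 × 88 = 59 to 135/176 × 88 = 68 patients.

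**3. Share among patients who reach NAD.** The bullet counts reactivation after NAD, so the mix at NAD is what matters. Section 2 gives the probability of NAD in LCH-II as 57% for Risk and 84% for Low Risk patients. Assume that the children without risk organs reach NAD with probability n between these values. Then s = w × n / 0.57:
- w = 23.3%: s = 23.3% (n = 57%) to 34.3% (n = 84%)
- w = 33.0%: s = 33.0% to 48.6%

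**4. Implied rate in risk-organ patients.** Section 2 gives 2-year reactivation after NAD as 64% for Risk and 56% for Low Risk patients. Let u be the rate in the children without risk organs, which is not given. Then r = (0.64 − s × u) / (1 − s). For example, with s = 0.343 and u = 0.56, r = (0.64 − 0.192) / 0.657 = 0.682.

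| s | u = 45% | u = 56% | u = 64% | u = 75% |
|---|---|---|---|---|
| 23.3% | 69.8% | 66.4% | 64.0% | 60.7% |
| 34.3% | 73.9% | 68.2% | 64.0% | 58.2% |
| 33.0% | 73.3% | 67.9% | 64.0% | 58.6% |
| 48.6% | 81.9% | 71.6% | 64.0% | 53.6% |

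At u = 56%, the unrestricted 64% is too low by 2.4 to 7.6 points. Over u = 45% to 75%, the error runs from 17.9 points too low to 10.4 points too high. It is zero at u = 64% and changes sign there.

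**5. Limits of the inputs.** The 57% and 64% are given for LCH-II Risk patients, with no statement that they are confined to randomised patients or to Arm A. Applying the randomised shares to them is an approximation.

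**The case against.** The strongest reply is that the bullet opens by limiting itself to Risk patients. In this protocol that is a defined term meaning risk-organ involvement, and on that reading both sides are already restricted. The authors also subset LCH-II by risk organ elsewhere. Section 2 isolates the 118, and the 50% control rate in Section 16.5.1 matches the figure given for that subset. Section 16.6 uses 50 patients from Arm A of LCH-II although 88 were randomised to it, so naming the arm need not mean the whole arm.

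This reading is open, and a reader who infers that the plan commits to all of LCH-II Arm A goes further than the text. But the text does not settle the matter. In the LCH-II sense, the limitation to Risk patients removes nobody from that arm. The adjacent bullet spells out organ status where this one does not. Section 16.6 does not say how its 50 were chosen.

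A reader might also infer that a lower-risk control must make longer treatment look worse than it is. The documents do not support that. The 56% comes from LCH-II Low Risk patients, who were over 2 years old. Section 2.1's statement that young age without risk organs does not carry a poor outcome follows a discussion of deaths and gives no reactivation rate.

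It is also fair to say that selection of historical controls for an exploratory analysis is often left to a statistical analysis plan, and that course 2 is openly listed as a separate change. That keeps the point minor. It does not repair wording that names a control without the needed restriction and credits the result to duration.

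**Conclusion.** The point holds as a mismatch in the control as named. Between 23% and 33% of randomised LCH-II Risk patients would not qualify for LCH III Group 1, or about 20 to 29 of the 88 in Arm A under an even split. If these children had the Low Risk reactivation rate and reached NAD at between 57% and 84%, the unrestricted figure would understate the risk-organ control rate by about 2 to 8 points. That is an illustration under stated assumptions. Without their actual rate, neither direction nor size is fixed. The course 2 point also holds, as a matter of how the contrast is described.

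The importance is low. Section 16.3 makes secondary analyses exploratory, no power is attached to this one, and the primary endpoint tests are untouched.

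**What to change.** In Section 16.2.2, name the control as Arm A of LCH-II, restricted to patients with RISK organ involvement as defined in 4.4.1. Describe the contrast as prolonged treatment together with course 2, not as duration alone.

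The cost is a wording change and about 20 to 29 fewer historical controls, leaving roughly 59 to 68. Section 2 already reports LCH-II results by risk-organ status, so the classification exists.

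It may be tempting to isolate duration by showing separately the patients who were NAD at week 6 and so skipped course 2. I would not add this, because it selects on response after treatment has started.

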## **16.3 ANALYSES**

The analyses of the primary and secondary endpoints will be done according to the intention-to-treat principle, i.e. the patients will be analyzed in their allocated treatment group, even in case of non-compliance or protocol violations.

The statistical analyses of the primary endpoint will be done with a two-sided significance level of 5 %. The statistical analyses of the secondary endpoints are exploratory. A separate analyses will be performed for each group (“RISK” and “LOW RISK”). In addition to the intention-to-treat analyses a secondary per protocol analyses will be done including all patients who were treated according to the originally assigned treatment arm without protocol violations (= unjustified dose modification, therapy delay and/or improper switch to another therapy within the first 12 months).

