### **9.1.2.3 Continuation treatment**

Continuous oral 6-mercaptopurine (6-MP) 50mg/m^2 until the end of month 12 from therapy start.

Pulses of oral prednisone PDN 40mg/m^2 in 3 doses, day 1-5 q 3 weeks, starting at day 1 of week 7 in patients NAD after course 1 or at day 1 of week 13 in patients NAD or

AD better after course 2 until the end of month 12.

Methotrexate 20mg/m^2 orally, once weekly until the end of month 12.

Vinblastine (VBL) 6mg/m^2 i.v. bolus, day 1 q 3 weeks, starting at day 1 of week 7 in patients NAD after course 1 or at day 1 of week 13 in patients NAD or AD better after course 2 until the end of month 12.

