#### **16.3.1.2 Group 2 “LOW RISK” patients:**

Reactivation (=progression in any organs) and death will be considered as events for the calculation of Reactivation Free Survival. The interval will start 6 months after therapy start, i.e. the time point when half of the patients are intended stop the continuation therapy (Arm LR6) whereas patients from the other randomized arm (Arm LR12) will further receive 6 months of continuation therapy. This means, randomized patients with reactivations within the first 6 months after randomization will not be included in the analyses. For censored patients the interval will be calculated until the date of the last response evaluation.

The proportion of reactivation free survival will be estimated according to the method of Kaplan-Meier and confidence intervals according to Dorey and Korn will be given for the reactivation free survival rate after 2 and 3 years. The primary statistical evaluation of the treatment effect will be done by log rank-test.

As a secondary aim the question whether a prolonged therapy can slow down the speed of reactivation will be considered. Retrospective data from LCH-I and LCH-II and the DAL-studies indicate that the hazards between 6 and 12 months of continuation therapy are proportional and constant in time (i.e. exponentially distributed reactivation free survival times). Therefore, a Weibull accelerated failure time model will be fitted to evaluate an acceleration factor. Moreover, a time dependent Cox regression model will be performed.

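### The per-protocol set counts violations to month 12, but the Group 1 endpoint is settled by week 12, so later exclusions fall almost only on responders and inflate the per-protocol non-response rates

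*Protocol*

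**What the plan says.** Protocol 16.3 makes intention-to-treat the analysis of the primary and secondary endpoints and then adds: "In addition to the intention-to-treat analyses a secondary per protocol analyses will be done". The per-protocol set keeps patients treated as assigned without violations, and violations are "unjustified dose modification, therapy delay and/or improper switch to another therapy within the first 12 months". The section also states that "A separate analyses will be performed for each group", but gives no separate per-protocol definition by group or by endpoint.

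Protocol 16.2.1.1 sets the Group 1 primary endpoint as the proportion of "non-responder in risk organs to the initial treatment". It has three components: "death within 12 weeks of initial treatment or" "progression (worse) in risk organs at week 6", or lack of response in risk organs at week 12. Each is known by week 12.

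Protocol 10.3.1 sends patients who are worse at week 6, or intermediate or worse at week 12, to salvage. Section 11, on leaving the study, also directs patients with risk-organ progression after course 1 or 2 to salvage. Responders stay on assigned treatment to month 12 (9.1, 9.1.1.3, 9.1.2.3).

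For Group 2, Protocol 16.3.1.2 says of reactivation free survival: "The interval will start 6 months after therapy start".

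**The concern.** Membership of the per-protocol set depends on about 40 weeks of behaviour (52 - 12) after the Group 1 outcome is known. Who is still exposed to the violation criteria in those weeks depends on the outcome itself. A patient who died by week 12 cannot breach the regimen, and one moved to salvage as directed is no longer on it. A responder has the whole continuation phase in which to be excluded. The set therefore loses responders selectively, and the per-protocol non-response proportion is pushed upwards in each arm.

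At stake is how the secondary analysis is read. If per-protocol and intention-to-treat results differ, part of the difference may come from the way the set was built and not from adherence.

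Reading the 12-month limit as applying only to improper switches does not help, because dose modifications and delays would then have no time limit at all.

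**Working it through.** **Inputs.** Non-response 50% in arm A and 30% in arm B, two-sided 5%, power above 80%, fixed-design total 202, group sequential maximum 228 (Protocol 16.5.1). Fisher's exact test (16.3.1.1). Assumptions: 1:1 allocation, and q, the share of responders removed for violations after week 12. The protocol gives no violation rates, so q is shown over a range.

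**The plan's own figure.** Exact two-sided Fisher power for 50% v 30% is 79.9% with 101 per arm and 80.6% with 102 per arm. The stated 202 is reproduced to within one patient per arm.

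**Formula.** If true non-response is p, a share q of responders is removed after week 12 and no non-responder is, then

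per-protocol non-response = p / (p + (1 - p)(1 - q)).

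The odds of non-response in each arm are multiplied by 1/(1 - q), so the A-to-B odds ratio is multiplied by (1 - qB)/(1 - qA). At the design rates the true odds ratio is (0.5/0.5)/(0.3/0.7) = 2.33.

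**Equal removal in both arms**

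| q | Arm A | Arm B | Difference (points) | Odds ratio |
|---|---|---|---|---|
| 0 | 50.0% | 30.0% | 20.0 | 2.33 |
| 10% | 0.5/0.95 = 52.6% | 0.3/0.93 = 32.3% | 20.4 | 2.33 |
| 20% | 0.5/0.90 = 55.6% | 0.3/0.86 = 34.9% | 20.7 | 2.33 |
| 30% | 0.5/0.85 = 58.8% | 0.3/0.79 = 38.0% | 20.9 | 2.33 |

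Both rates are overstated, while the comparison hardly moves.

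**Unequal removal**

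- 15% in A, 30% in B: 0.5/0.925 = 54.1% v 38.0%, difference 16.1 points, odds ratio 2.333 × 0.70/0.85 = 1.92.
- 20% in A, 10% in B: 55.6% v 32.3%, difference 23.3 points, odds ratio 2.333 × 0.90/0.80 = 2.63.

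The bias can go either way.

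**No true effect.** Take 50% in both arms, 114 per arm (228/2) before exclusions, and a single fixed Fisher test. With 10% removed in A and 30% in B, the per-protocol rates are 52.6% v 58.8%, a spurious 6.2 points. The test rejects in 13.2% of trials, against 4.0% with no exclusions. With 10% removed in both arms it rejects in 3.45%.

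**If some non-responders are also removed.** Removing 5% of non-responders along with 20% of responders gives 0.475/0.875 = 54.3% and 0.285/0.845 = 33.7%. The inflation shrinks but remains.

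**Group 2, for scale.** Assume exponential reactivation free survival of 85% at one year in LR 12 (the target in 16.5.2), counted from month 6. Assume also that 20% of patients are removed for violations in months 6-12, but half that share among those with an event in those months. Events in the first half year: 1 - 0.85^0.5 = 7.8%; in the second half year: 7.2%. Retained: 7.8% × 0.9 + 7.2% × 0.8 + 85% × 0.8 = 80.8%. One-year rate: 68.0/80.8 = 84.2%. The shift is under one point.

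**The case against.** The strongest answer is that no decision rests on this analysis. It is secondary. The intention-to-treat Fisher test, its 5% level, the sample sizes of 202 and 228 and the interim boundaries are all untouched. That stands, and it limits the weight of the point.

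A reader might infer that non-responders cannot be excluded at all. The protocol does not support this. Any patient can be excluded for a violation before the endpoint. A non-responder kept on protocol drugs, or moved to some other therapy, could also be judged an improper switch. Only deaths are fully immune, so the accurate statement is that late exclusions fall almost only on responders.

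A reader might also infer that arm B must lose more responders, because its continuation phase adds weekly oral methotrexate (9.1.2.3). That is possible but not established. Only unjustified changes count, and Protocol 9.6 itself directs holds and reductions of oral mercaptopurine and methotrexate, so those are not violations. No violation rate is given for either arm, and the direction of any imbalance is unknown.

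For Group 2, a reader might infer that LR 6 patients have nothing to breach after month 6. They do: responders are assigned to stop at month 6 (10.3.2), and continuing without reason would breach that. Months 6-12 are also where the two arms differ, so a 12-month adherence window has a rationale there. What remains is that exclusion in those months can depend on follow-up after the clock has started.

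Finally, per-protocol details are often left to a SAP, which is not at hand. Here, however, the protocol states a specific window, and that window does not fit the week-12 endpoint.

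**Conclusion.** The point holds for the secondary per-protocol analysis of Group 1 response. The upward bias in each arm's non-response rate follows from the exclusion window, the endpoint definition and the route to salvage. Its size depends on the share of responders removed. For 10% to 30% removed equally, the rates rise by 2.6 to 8.8 points in arm A and 2.3 to 8.0 points in arm B, with the odds ratio unchanged. Bias in the arm comparison requires unequal removal. The examples of 16.1 and 23.3 points against a true 20 show both directions and rest wholly on assumed rates. For Group 2 this is a limitation to note, not a demonstrated distortion of the result.

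**What to change.** In Protocol 16.3, give the per-protocol analysis of the Group 1 week-6 and week-12 response endpoints its own window: count only violations up to the earlier of non-response or the week-12 response assessment. Keep the 12-month window for the longer-term endpoints, where it matches the length of treatment. Under this rule, behaviour after the endpoint can no longer alter the per-protocol response rates. A smaller asymmetry remains, because patients who die early or progress at week 6 have a shorter window than those assessed at week 12.

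For Group 2, add a sentence stating as a limitation that violations in months 6-12 fall after the start of the reactivation free survival interval, so exclusion can depend on follow-up.

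The cost is wording only. Applying the existing 12-month rule already requires the dates of violations.
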